### **6.2 Bioanalytical Method**

Serum concentrations of TRL345 will be determined using an ELISA validated with respect to accuracy, precision, linearity, sensitivity, and specificity at Celerion, Lincoln, Nebraska. The analytical range (lower limit of quantitation [LLOQ] – upper limit of quantitation [ULOQ]) for TRL345 will be determined during validation of the ELISA.

### **6.3 Pharmacokinetic Concentrations**

#### **Measurements and Collection Schedule**

Blood samples for the determination of TRL345 in serum will be collected for all subjects at the following time points:

- Day 1: Predose (imputed as time 0) and approximately 1 hour  $\pm$  15 minutes (end of infusion [EOI]), 2 hours  $\pm$  15 minutes, 4 hours  $\pm$  15 minutes, 6 hours  $\pm$  15 minutes, and 12 hours  $\pm$  15 minutes post-start of infusion (SOI)
- Days 2 (24 hours  $\pm$  1 hour post-SOI), 3 (48 hours  $\pm$  1 hour post-SOI), 8 (168 hours post-SOI), 15 (336 hours post-SOI), 29 (672 hours post-SOI), 43 (1008 hours post-SOI), and 76 (1800 hours post-SOI)

All concentration data, as received from the bioanalytical lab, will be listed by subjects, treatment, and nominal time in an appendix. If there are any significant protocol deviations (e.g., significant time deviations from nominal sample times), some individual concentration data may be excluded from mean data presentations (e.g., descriptive statistics for concentrations at specific nominal time points and mean concentration-time plots). No concentration values will be imputed for missing or not reported samples (NS or NR), unless predose. All deviations and excluded data will be provided and discussed in the CSR.

### **6.4 Noncompartmental Pharmacokinetic Analysis and Parameter Calculation**

#### **6.4.1 Serum TRL345 Pharmacokinetic Parameters**

The appropriate noncompartmental PK parameters will be calculated from the serum TRL345 concentration-time data using Phoenix® WinNonlin® Version 8.3.4 or higher. Actual sample times will be used in the calculations of the PK parameters. The calculation of the actual time for TRL345 will be in respect to the SOI of TRL345 on Day 1. All PK

parameters included in the protocol are listed in [Table 6–1](#) below, and are defined as appropriate for study design.

**Table 6–1 Noncompartmental Serum TRL345 Pharmacokinetic Parameters to be Calculated**

Parameter	Label to be Used in the Text, Tables, and Figures*	Definition	Method of Determination
AUC 0-tlast	AUClast	Area under the concentration-time curve from time 0 to the time of the last observed/measured non-zero concentration	Calculated using the Linear Trapezoidal with Linear Interpolation Method
AUC 0-inf	AUC0-inf	Area under the concentration-time curve from time 0 extrapolated to infinity	Calculated as $AUC_{0-inf} = AUC_{0-tlast} + (C_{last}/K_{el})$ where Clast is the last observed/measured concentration
AUC%extrap	AUC%extrap	Percent of AUC0-inf extrapolated	Calculated as $AUC\%extrap = (1 - (AUC_{0-tlast}/AUC_{0-inf})) \times 100$
C coi	Ccoi	Concentration at the end of infusion	Taken directly from bioanalytical data
C min	Cmin	Minimum observed concentration following a single dose corresponding to the single IV dose administration	Taken directly from bioanalytical data
C max	Cmax	Maximum observed concentration	Taken directly from bioanalytical data
T min	Tmin	Time of minimum observed concentration (Cmin) following a single dose corresponding to the single IV dose administration	Taken from clinical database as the difference in the time of administration and the time of the blood draw which is associated with the Cmax
T max	Tmax	Time to reach Cmax; if Cmax occurs at more than 1 time point, Tmax is defined as the first time point with this value	Taken from clinical database as the difference in the time of administration and the time of the blood draw which is associated with the Cmax
T last	Tlast	Time of the last measurable concentration	Taken from clinical database as the difference in the time of administration and the time of the blood draw which is associated with the Clast
λ z	Kel	Apparent first-order terminal elimination rate constant	The negative of the slope of a linear regression of the log(concentration)-time curve for all concentrations > LLOQ
t ½	t½	Apparent first-order terminal elimination half-life	Calculated as $t_{1/2} = 0.693/K_{el}$

Parameter	Label to be Used in the Text, Tables, and Figures*	Definition	Method of Determination
CL	CL	Total serum clearance after IV administration	Calculated as CL = Dose/(AUC0-inf)
Vss	Vss	Apparent volume of distribution estimated at steady state following a single IV dose administration	Calculated as Vss = MRT0-inf • CL

\*In the text of the CSR, subscripts will be used in parameter names, as appropriate. However, in post-text tables and listings, subscripts will not be used in parameter names.

PK parameters will not be calculated for subjects with less than 3 consecutive postdose time points with quantifiable concentrations. Subjects for whom there are insufficient data to calculate the PK parameters will be included in the concentration tables and individual concentration-time figures and flagged to exclude from the summaries.

For the calculation of the PK parameters, serum concentrations below the limit of quantitation (BLQ) prior to the first quantifiable concentration will be set to 0 and serum concentrations BLQ after the first quantifiable concentration will be treated as missing.

The Kel will be determined using linear regressions composed of at least 3 data points. Furthermore, the Kel will not be assigned if 1) the terminal elimination phase is not apparent, 2) Tmax is one of the last 3 data points, or 3) the R^2 value is less than 0.75. In cases where the Kel interval is not assigned, the values of Kel and Kel-dependent parameters (i.e., AUC0-inf, AUC%extrap, t1/2, CL, and Vss) are considered not calculable and will not be reported. Wherever the resulting t1/2 is more than half as long as the sampling interval, the Kel value and Kel-dependent parameters (i.e., AUC0inf, AUC%extrap, t1/2, CL, and Vss) may not be presented, as judged appropriate and in accordance with Celerion standard operating procedures (SOPs).

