2 OBJECTIVES AND ENDPOINTS

2.1 Objectives

2.1.1 *Primary Objective*

- Assess the safety and tolerability of TRL345 when administered intravenously (IV) as a single dose in healthy adult volunteers

2.1.2 *Secondary Objectives*

The secondary objectives are to:

- Characterize the pharmacokinetics (PK) of a single IV infusion of TRL345 overall and by DG
- Assess the immunogenicity of TRL345 as measured by anti-drug antibodies (ADAs)

2.1.3 *Exploratory Objective*

The exploratory objectives are to:

- Explore the pharmacodynamics (PD) of TRL345 in an *ex vivo* study using serum samples to explore the capacity of various concentrations of TRL345 to neutralize HCMV in human serum
- Explore if there are any differences in adverse events, clinical labs, or PK across dose groups to explore if there are any signs of off-target binding of TRL345

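### The linear trapezoidal rule in SAP Table 6–1 overstates AUC by a few per cent; a log rule for the decline, with MRT and Kel properly defined, removes most of the resulting error in CL and Vss

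*SAP*

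**What the plan says.** The secondary PK objective is to "Characterize the pharmacokinetics (PK) of a single IV infusion of TRL345 overall and by DG" (Protocol 2.1.2). Protocol 2.2.2 and SAP Section 2 name CL and Vss among its endpoints. Protocol 2.2.5 adds estimated AUC as a comparator across dose groups when looking for off-target binding.

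SAP 6.3 places draws at predose, 1, 2, 4, 6, 12, 24 and 48 h, then on Days 8 (168 h), 15 (336 h), "29 (672 hours post-SOI), 43 (1008 hours post-SOI), and 76 (1800 hours post-SOI").

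The calculations are in SAP Table 6–1:

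- AUC0-tlast: "Calculated using the Linear Trapezoidal with Linear Interpolation Method".
- AUC0-inf: AUC0-tlast plus Clast/Kel, "where Clast is the last observed/measured concentration".
- CL: dose divided by AUC0-inf.
- Vss: "Calculated as Vss = MRT0-inf • CL". Neither MRT0-inf nor AUMC is defined.
- Kel: the table row fits the log-linear regression to every concentration above the quantification limit. The text under the table speaks of a terminal elimination phase and requires at least three points. The two differ.

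SAP Section 9, which lists departures from the protocol, does not mention the integration rule.

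**The concern.** Linear interpolation does little harm where samples are close together. Here the late samples are days to weeks apart, and that is where most of an antibody's AUC lies. The protocol leads one to expect an exponential shape: Protocol 1.3.2 reports that a two-compartment model described the rat data accurately. The SAP itself assumes log-linear decline when it estimates Kel and extrapolates the tail, but not when it integrates between samples.

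An AUC error passes directly into AUC0-inf and CL, and through CL and MRT into Vss. It does not shrink with more subjects, and no reported SD or CV% would reveal it. It also varies with half-life and with which sample is the last quantifiable one, so it need not be identical in the two dose groups.

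**Working it through.** **Inputs from the documents.** A 1-h infusion, the nominal times above, the Table 6–1 formulas and six active subjects per dose group. Late gaps: (168 − 48)/24 = 5 days, then 7, 14 and 14 days, then (1800 − 1008)/24 = 33 days. The plan states no bias or precision figure, so there is nothing of its own to reproduce.

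**Assumptions.** No human PK values are readable in the documents. The example uses V1 3 L, V2 2.5 L, Q 0.4 L/day and CL 0.30, 0.20 or 0.15 L/day, which give terminal half-lives of about 15, 21 and 28 days. Data are error-free, AUMC uses the same rule as AUC, and MRT = AUMC/AUC − 0.5 h.

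**One segment.** For a mono-exponential decline over a gap d with half-life h, let x = d·ln 2/h. The linear area divided by the true area is (x/2)(1 + e^−x)/(1 − e^−x). For the 33-day gap:

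- h = 14: x = 1.634, ratio 1.213.
- h = 21: x = 1.089, ratio 0.5446 × 1.3365/0.6635 = 1.097.
- h = 28: x = 0.817, ratio 1.055.

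These percentages apply to a segment that holds little of the total area.

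**Whole profile, terminal-phase Kel, errors against the true value.**

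| Half-life | Rule | AUC0-inf | CL | Vss |
|---|---|---|---|---|
| 15 d | linear | +5.7% | −5.4% | −10.6% |
| 21 d | linear | +3.7% | −3.6% | −8.1% |
| 28 d | linear | +2.6% | −2.5% | −6.1% |
| 15 d | log-down | +1.5% | −1.5% | −2.3% |
| 21 d | log-down | +1.1% | about −1% | −1.8% |
| 28 d | log-down | +0.8% | −0.8% | −1.4% |

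Taking Kel from the last three points or using the true slope makes no material difference. Vss moves more than CL because linear AUMC is itself slightly low (0.2% to 1.2%), so MRT is short as well.

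**Where the AUC error arises.** Day 43–76 contributes 1.0 to 1.7 percentage points and Day 3–8 contributes 0.7 to 1.8. The other intervals make up the rest.

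**Wider range.** For half-lives of 10 to 35 days, mono- or bi-exponential, the linear rule gives AUC0-inf +1.0% to +7.5%, CL −1.0% to −7.0% and Vss −2.9% to −11.9%. Log-down gives 0 to +2.1%, 0 to −2.0% and 0 to −3.3%, with zero error for a mono-exponential decline. As an outer bound, the rat half-life of 46 h would give AUC about +14% to +15%.

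**Kel from all points, as the table row reads.** Under the linear rule CL is off by −4.8%, −1.6% and +1.7% at 15, 21 and 28 days. At 28 days, switching to log-down alone moves CL from +1.7% to +3.6%.

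**Dose-group contrast.** A true twofold CL ratio (0.30 to 0.15) is estimated as (0.30 × 0.946)/(0.15 × 0.975) = 1.94. A true ratio of 1.33 (0.20 to 0.15) comes out as 1.32. If Day 76 is below quantification only at the lower dose, the CL error there at 14 to 28 days is −0.4% to −3.8% instead of −1.5% to −5.6%, an artefact of about 1 to 2 points.

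**Precision.** The standard error of a mean of six is 20%/√6 = 8.2% to 30%/√6 = 12.2% at an assumed CV of 20% to 30%.

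**The case against.** The strongest reply is that this is too small to matter. PK results are summarised descriptively (Protocol 8.2 and 8.6). No test or threshold uses AUC, CL or Vss, and escalation rests on safety data (Protocol 3.5). Both groups share one schedule, so most of the error cancels between them. Half-life, the other PK comparator, comes from log regression and does not depend on the trapezoid. The CL error lies inside the standard error. All of this stands, and it limits the weight of the point.

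A reader might also infer three stronger things that the documents do not support:

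- **That the sampling design is at fault, the 33-day gap above all.** A log rule on the same draws removes most or all of the error, and the Day 3–8 gap contributes about as much as the last one.
- **That CL and Vss are understated in every case.** CL needs a terminal-phase Kel. With Kel fitted to all points, the net CL error can change sign. The size of the Vss error depends on how AUMC is computed, which the SAP leaves open. Only the upward contribution to AUC is unconditional for such a decline.
- **That the search for off-target binding is undermined.** The attenuation is about 1% to 3% in the examples above.

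**Conclusion.** The point holds as a modest, systematic and avoidable error in how AUC is integrated, and it is worth correcting because doing so costs almost nothing. The direction for AUC follows from the shape of the curve and is firm. The sizes for CL and Vss rest on an assumed human half-life, a terminal-phase Kel and linear AUMC, so they should be read as illustrations. On those assumptions log-down removes about 70% of the CL error and just over three quarters of the Vss error. It does not invalidate the secondary PK results or the dose-group comparison.

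**What to change.** Make three changes to SAP Table 6–1, together:

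1. For AUC, and for AUMC once it is added, specify Linear Up Log Down: linear while concentrations rise, logarithmic while they fall.
2. Define MRT0-inf as AUMC0-inf/AUC0-inf minus half the infusion time (0.5 h). The correction is numerically tiny here, but the definition is needed for Vss to be reproducible.
3. Reword the Kel row so that it uses the terminal-phase points, at least three, as the text under the table already describes.

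The third change should not be left out: with Kel fitted to all points, log-down alone can leave CL no better or worse. The cost is a short SAP edit and a software setting, with no additional samples, visits or change to the schedule.

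### The Kel row of SAP Table 6–1 uses all quantifiable concentrations, the surrounding text implies a terminal interval, and no rule selects the points; read literally, half-life comes out too short

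*SAP*

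**What the plan says.** SAP Section 6.4.1, Table 6–1, gives the method for Kel as "The negative of the slope of a linear regression of the log(concentration)-time curve for all concentrations > LLOQ". Half-life is 0.693/Kel and is defined as "Apparent first-order terminal elimination half-life".

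The text after the table reads differently:
- "The Kel will be determined using linear regressions composed of at least 3 data points".
- "the Kel will not be assigned if 1) the terminal elimination phase is not apparent, 2) Tmax is one of the last 3 data points". An R-squared below 0.75 has the same effect.
- The consequence of failing these conditions begins "In cases where the Kel interval is not assigned", so an interval is expected to be assigned.
- Appendix 16.2.6.2 (shell CPKel2) lists each subject's interval, R-squared and number of points.

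Another rule says that when half-life "is more than half as long as the sampling interval, the Kel value and Kel-dependent parameters" may be left out, as judged appropriate. The sampling interval is not defined. BLQ values after the first quantifiable one are treated as missing, and SAP Section 6.2 leaves the LLOQ to assay validation.

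Half-life, CL and Vss are secondary PK endpoints (Protocol 2.2.2, SAP Section 2). Estimated AUC and half-life are also compared across dose groups when looking for off-target binding (Protocol 2.2.5).

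**The concern.** The table row is the only sentence that says which concentrations enter the regression, and it does not limit them to the terminal phase. The later text sets a minimum number of points and grounds for refusing Kel, but no rule for choosing points. So either the row is followed and half-life is biased, or it is not followed and the points are picked by an unwritten rule.

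Kel feeds half-life, AUC0-inf, CL and Vss. A literal fit also becomes more weighted to distribution as late samples are lost. If that happened only at 1 mg/kg, half-life would look shorter at the low dose, which could be mistaken for a binding sink.

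**Working it through.** The documents give no human half-life, Kel or LLOQ, so there is no planned figure to reproduce. The check shows what the row does to a known curve.

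**Inputs from the documents.** Post-dose samples at 1, 2, 4, 6, 12, 24, 48, 168, 336, 672, 1008 and 1800 h (SAP 6.3); 1-h infusion of 1 or 10 mg/kg (SAP Section 5); two-compartment decline in the rat (Protocol 1.3.2).

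**Assumptions, not in the documents.** Terminal half-life 14, 21 or 28 days; distribution half-life 6, 24 or 48 h; distribution share *s* of the initial concentration 0.3, 0.5 or 0.7 (27 combinations); central volume 45 mL/kg; LLOQ 0.1 to 2 µg/mL; linear PK; no noise.

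**Direction.** After the infusion, C(t) = A·exp(−αt) + B·exp(−βt) with α > β. Then ln C(t) minus the terminal line equals ln[1 + (A/B)·exp(−(α−β)t)]. This excess falls with time, so its covariance with time is negative. The all-points slope is therefore always steeper than β, and half-life is always too short.

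**Worked example.** True half-life 21 days (504 h), distribution half-life 24 h, *s* = 0.5, so β = 0.693/504 = 0.001375 per h. The excess over the terminal line is 0.69, 0.67, 0.65, 0.62, 0.55, 0.42 and 0.24 at 1 to 48 h, 0.01 at 168 h, and about 0 afterwards.
- All 12 samples: slope = Sxy/Sxx = −6033/3,463,969 = −0.001742 per h. Half-life = 0.693/0.001742 = 398 h = 16.6 days (−21%), R-squared 0.949.
- Day 76 BLQ, 11 samples: −2325.1/1,138,853 = −0.002042 per h. Half-life = 339 h = 14.1 days (−33%), R-squared 0.920.
- Last three quantifiable points: 21.0 days in both cases.

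**All 27 combinations.**

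| Last quantifiable sample | All-points half-life error: worst / median / best | R-squared < 0.75 | Last-3 half-life error |
|---|---|---|---|
| 1800 h (Day 76) | −42 / −18 / −6% | 0 of 27 | about 0% |
| 1008 h (Day 43) | −56 / −29 / −10% | 1 of 27 | 0 to −4% |
| 672 h (Day 29) | −66 / −39 / −15% | 3 of 27 | 0 to −27% |

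With all samples, a true 21 days reads 16.1 to 19.3 days for *s* = 0.3 or 0.5, and 13.7 to 15.8 days for *s* = 0.7.

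**Clearance.** Relative to the last-3 fit, the all-points Kel raises CL by 0.1% to 5.7% with all samples, and by about 1% to 21% without Day 76. Half-life is affected much more.

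**Dose groups.** With linear PK and all samples quantifiable, the error is identical at 1 and 10 mg/kg. If only the 1 mg/kg group loses Day 76, the example gives 14.1 against 16.6 days, a ratio of 0.85, for the same true 21 days. The modelled 1 mg/kg concentration at Day 76 is 0.16 to 2.4 µg/mL across the combinations (0.94 in the example). An LLOQ of 0.1 µg/mL loses none of these samples; 1 to 2 µg/mL loses many.

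**Long half-life rule.** If the sampling interval is the full 1800 h (75 days), the cut-off is 37.5 days. If it is Day 29 to Day 76 (1800 − 672 = 1128 h = 47 days), the cut-off is 23.5 days. The text does not say which applies.

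**The case against.** The strongest reply is that the SAP does not intend an all-points fit. It names the parameter terminal, says that "the Kel will not be assigned if 1) the terminal elimination phase is not apparent", speaks of an assigned interval, and lists interval and number of points by subject. Those provisions would have little purpose if every point were used, and the table row can be read as a filter on which points are eligible. This stands as far as it goes: a reader might infer that the SAP unambiguously fits every point, and the documents do not support that. It does not supply the missing selection rule.

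Outputs already planned would help a reader notice trouble: Tlast, AUC%extrap, the number of subjects per parameter, and individual semi-log profiles. The comparison across dose groups is exploratory and half-life is one of several read-outs. With 6 active subjects per group and an assumed CV of 25%, the standard error of the log half-life ratio is 0.25 × √(2/6) = 0.14, about the size of the 15% artefact. These points limit the consequence. They do not remove a systematic error in a secondary endpoint.

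Three stronger readings fail:
- **A false binding sink is to be expected.** It needs both the literal fit and late BLQ loss confined to 1 mg/kg, and the LLOQ is unknown.
- **The AUC rule ("Calculated using the Linear Trapezoidal with Linear Interpolation Method") adds to the Kel error.** With the all-points Kel and full sampling, the smaller Clast/Kel term largely offsets the trapezoid excess. In assumed profiles with a 21-day half-life, the net AUC0-inf error is about +1% to +2%.
- **The long half-life rule will remove many subjects on top of the Kel bias.** Heavy removal needs the Day 29 to Day 76 interval, which implies a terminal three-point fit with almost no Kel bias. The two harms do not occur together.

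**Conclusion.** The concern holds as an internal contradiction plus a missing point-selection rule, and should be fixed. The direction of the error under a literal reading is certain for any two-compartment decline. Its size, about 6% to 42% with all samples and more if late samples are BLQ, rests on assumed human parameters and noise-free, linear curves. Accelerated late clearance, for example through anti-drug antibodies or target binding, could change the size or direction. The R-squared limit is not a dependable safeguard. A spurious dose-group difference is a conditional risk, not a prediction. The undefined sampling interval and the discretion to withhold long half-lives are secondary weaknesses.

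**What to change.** 1. Reword the Kel row in Table 6–1 as the slope over the terminal log-linear phase only. Use at least the 3 last quantifiable points after Tmax, exclude distribution-phase samples (stating how they are identified), and choose the points by best adjusted R-squared. Apply the same pre-specified rule in both dose groups.
2. Show Tlast and the number of fitted points by dose group beside half-life. The terminal rule alone is not a full cure: a last-3 fit also degrades when the last quantifiable sample is Day 29.
3. Secondary: define the sampling interval in the long half-life rule, and present flagged values instead of withholding them by judgement.
4. Optional: linear-up/log-down for AUC.

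The cost is SAP wording, a software setting and small additions to one PK table. No new samples or data are needed.

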## 6.5 Data Summarization and Presentation

All TRL345 serum concentrations and/or PK parameters descriptive statistics will be generated using SAS® Version 9.4 or higher.

The serum concentrations of TRL345 will be listed and summarized by dose group, treatment and time point for all subjects in the PK Population. Serum concentrations of TRL345 will be presented with the same level of precision as received from the bioanalytical laboratory (i.e., 3 significant figures). Summary statistics, including sample size (n), arithmetic mean (mean), standard deviation (SD), coefficient of variation (CV%), standard error of the mean (SEM), minimum, median, maximum, and range will be calculated for all nominal concentration time points. Excluded subjects or data will be included in the concentration listings but will be excluded from the summary statistics and noted as such in the tables. All BLQ values will be presented as “BLQ” in the concentration listings and tables but will be set to zero or missing as described in [Section 6.4.1](#) for the calculation of summary statistics and footnoted accordingly.

Mean and individual serum TRL345 concentration-time profiles will be presented on linear and semi-log scales. Individual concentration-time profiles will be based on actual sample times, and mean concentration-time profiles will be based on nominal sample times. Linear mean plots will be presented with and without SD. When there are significant (> 3%) time deviations from nominal sample time points, some concentrations may be excluded from the summary statistics and any corresponding summary figures.

TRL345 PK parameters will be listed and summarized by treatment for all subjects in the PK Analysis Population. PK parameters will be reported to 3 significant figures for individual parameters, with the exception of Cmax, (Ceoi, if warranted) and Cmin which will be presented with same level of precision as received from the bioanalytical laboratory and Tmax, which will be presented with 2 decimal places. Summary statistics (n, mean, SD, CV%, SEM, minimum, median, maximum, range, geometric mean (Geom Mean), and geometric CV% (Geom CV%)) will be presented for all PK parameters. Excluded subjects will be listed in the PK parameter tables, but will be excluded from the summary statistics and noted as such in the tables.

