CV%	.	XX.X	XX.X	XX.X	XX.X	XX.X	XX.X	XX.X	XX.X
SEM	XX.XX	XX.XX	XX.XX	XX.XX	XX.XX	XX.XX	XX.XX	XX.XX	XX.XX
Minimum	XX	XX	XX	XX	XX	XX	XX	XX	XX
Median	XX.X	XX.X	XX.X	XX.X	XX.X	XX.X	XX.X	XX.X	XX.X
Maximum	XX	XX	XX	XX	XX	XX	XX	XX	XX
Range	XX	XX	XX	XX	XX	XX	XX	XX	XX

For the calculation of summary statistics, values that are below the limit of quantitation (BLQ) of X.XX ug/mL are treated as 0 before the first quantifiable concentration and as missing elsewhere.  
 . = Value missing or not reportable

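### If any late sample is BLQ, the SAP's BLQ-as-missing rule biases late concentration summaries and Cmin upward; separately, the Tmin method cell points to the Cmax draw

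*SAP*

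**What the plan says.** **BLQ rule.** For PK parameters, SAP 6.4.1 sets BLQ values before the first quantifiable one to zero; after it, "serum concentrations BLQ after the first quantifiable concentration will be treated as missing". SAP 6.5 extends this to the concentration summaries: BLQ is printed as text "in the concentration listings and tables but will be set to zero or missing as described in" Section 6.4.1. The footnote to shell CPConc1 (SAP 11.3) repeats that, in the summary statistics, such values "are treated as 0 before the first quantifiable concentration and as missing elsewhere".

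**Cmin.** Table 6–1 defines it as "Minimum observed concentration following a single dose corresponding to the single IV dose administration", read from the bioanalytical data, with no BLQ rule of its own. Cmin is a secondary PK endpoint in Protocol 2.2.2 and SAP Section 2. The in-text parameter table reports it as a geometric mean with geometric CV%.

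**Tmin.** The definition column of Table 6–1 gives "Time of minimum observed concentration (Cmin) following a single dose corresponding to the single IV dose administration". The method column gives "Taken from clinical database as the difference in the time of administration and the time of the blood draw which is associated with the Cmax", which is word for word the method in the Tmax row.

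**LLOQ.** No value is given; SAP 6.2 says the analytical range "for TRL345 will be determined during validation of the ELISA".

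**The concern.** A post-dose BLQ result is not missing information. It says that the concentration was lower than every quantifiable value. Ignoring it is a common convention for AUC and for the terminal slope. In a summary at a late nominal time it means averaging only the subjects who still have measurable drug. With six active subjects per dose group, each dropped value is one sixth of the data.

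Cmin is affected more directly. If the lowest sample is BLQ and is discarded, the reported minimum is the next value up, usually from an earlier visit. At equal clearance the 1 mg/kg group reaches the LLOQ before the 10 mg/kg group, so the two groups' tables may not be affected equally.

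Tmin is a smaller matter. It is not a protocol endpoint, but it is a planned row in the in-text and Section 14 parameter tables, so an error in its derivation would reach the study report.

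**Working it through.** The plan states no figure on this point, so there is nothing to reproduce. The check has four parts.

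**1. Effect on the late-visit mean.** From the SAP: 6 active subjects per group. Assumed: lognormal concentrations at one nominal time, between-subject CV 30, 50 or 70%, and a fraction p = 1/6, 2/6 or 3/6 below the LLOQ. With s = √ln(1 + CV²) and z = Φ⁻¹(p), relative to the true mean:

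- BLQ dropped: Φ(s − z) / (1 − p)
- BLQ set to LLOQ/2: Φ(s − z) + (p/2) × exp(sz − s²/2)

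Example, CV 50% and p = 1/6: s = 0.472, z = −0.967, Φ(1.440) = 0.925. Dropping gives 0.925 / 0.833 = 1.11. For LLOQ/2, exp(sz − s²/2) = 0.566, so the ratio is 0.925 + 0.566/12 = 0.97.

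| BLQ of 6 | Dropped (CV 30 / 50 / 70%) | LLOQ/2 (CV 30 / 50 / 70%) |
|---|---|---|
| 0 | 0 | 0 |
| 1 | +8 / +11 / +13% | −4 / −3 / −2% |
| 2 | +15 / +23 / +28% | −9 / −6 / −4% |
| 3 | +23 / +36 / +47% | −15 / −9 / −6% |

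**2. When BLQ values would occur.** In simulated groups of six at CV 50%, the ratio of the mean after dropping to the true mean depends on the geometric mean relative to the LLOQ:

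- 0.5 × LLOQ: 2.25 (93% of values BLQ; all six BLQ in 64% of groups)
- 1 × LLOQ: 1.36
- 2 × LLOQ: 1.05
- 4 × LLOQ or more: 1.00 (at most 1.02 at CV 80%)

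The readable text gives no human half-life. For illustration, take one-compartment decay with V = 60 to 305 mL/kg (the rat values in Protocol 1.3.2, used as an assumption). Day 76 (1800 h) concentrations after 1 mg/kg are then:

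| Assumed half-life | Day 76, µg/mL |
|---|---|
| 7 days | 0.002–0.010 |
| 14 days | 0.08–0.41 |
| 21 days | 0.28–1.4 |
| 28 days | 0.51–2.6 |

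Under linear kinetics, 10 mg/kg gives ten times these values. Whether any of them is BLQ depends on the LLOQ.

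**3. Effect on Cmin and AUC.** Assume 1 mg/kg, V = 60 mL/kg and LLOQ 0.1 µg/mL, with C(t) = (1/0.06) × 2^(−(t − 1)/t½) and t in hours.

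- Half-life 7 days (168 h): Day 43 (1008 h) is 0.261 and Day 76 is 0.010, which is BLQ. Dropping it gives a reported Cmin of 0.261, about 26 times the true minimum. AUC0-tlast by linear trapezoid is 4199 µg·h/mL, against 4307 with all true values, so it is not overstated.
- Half-life 14 days: Day 76 is 0.407, above the LLOQ. There is no BLQ value and no bias.

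**4. Tmin.** In both profiles Cmax is at 1 h. The method column gives Tmin = 1 h; the definition column gives 1008 h (7 days, after the BLQ drop) or 1800 h (14 days).

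**The case against.** **The bias is conditional.** It needs at least one post-dose BLQ value, and nothing in the documents shows that one will occur. If the assay is sensitive relative to Day 76 concentrations, the rule does nothing. This stands, and the point is stated conditionally for that reason.

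**The handling is disclosed.** CPConc1 prints each subject's row with BLQ shown, gives n at each time and footnotes the rule; with six subjects a reader can count the BLQ cells. That mitigates the problem, but the printed mean, median and minimum are still computed without the low values, and the Cmin summary carries no such flag.

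**Cmin is read directly from laboratory data.** One could therefore expect it to appear as BLQ. But the 6.4.1 rule covers the PK parameters without exempting Cmin, and the planned geometric mean has no provision for a BLQ entry. At best this is an ambiguity to resolve.

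**Tmin is a copy error.** Very probably. The definition beside it is correct, and a programmer may follow that. It still needs correcting, but adds no weight to the BLQ point.

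**Stronger readings that the documents do not support.** A reader might infer that exposure in general is overstated. AUC0-tlast runs "from time 0 to the time of the last observed/measured non-zero concentration", and the worked case shows it slightly low. A reader might also infer that the off-target comparison between dose groups is distorted. Its PK items in Protocol 2.2.5 are estimated AUC and half-life, not Cmin or late mean concentrations, and neither is shown to be biased here. Finally, a subject who leaves early may have a high Cmin simply because sampling stopped. That is unrelated to BLQ handling and is partly covered by the case-by-case review of incomplete data in SAP Section 4.

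**Conclusion.** The point holds in conditional form. The SAP removes post-dose BLQ values from the concentration summaries and from Cmin. The direction is certain whenever such a value occurs: the retained values are all higher, so the late mean, median and minimum and the affected subject's Cmin move up. The size for the mean rests on the lognormal shape and CV range assumed in the table. The 26-fold Cmin example rests on an assumed half-life, volume and LLOQ, and shows what can happen, not what is expected. The Tmin contradiction rests on no assumption, but it yields a wrong result only if the method column is followed. Both matters deserve correction before the concentration data arrive; neither threatens the primary safety objective.

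**What to change.** 1. In Table 6–1, change the Tmin method to the draw associated with Cmin.
2. In SAP 6.4.1, confine BLQ-as-missing after the first quantifiable value to AUC and Kel. Remove its extension in SAP 6.5 and in the CPConc1 footnote.
3. In the concentration summaries, rank post-dose BLQ values lowest for the median and minimum, show the number BLQ at each time, use LLOQ/2 for the mean, and suppress the mean when half or more are BLQ.
4. List Cmin as `<LLOQ` when a post-dose sample is BLQ, and summarise it by median and range. If a geometric mean is also shown, use LLOQ/2 with a footnote; setting BLQ to zero would leave the geometric mean undefined.

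The cost is SAP wording, two footnotes and minor programming. The statistical downside is that LLOQ/2 understates the mean by about 2–9% when 1–2 of 6 are BLQ. At 3 of 6 the understatement would be about 6–15%, but the mean is suppressed there. Protocol 8.2 rules out imputing missing data, so the SAP should say that a BLQ result is a reported, censored value and not a missing one.
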